5.2 Study population

Women with insomnia disorder in a standard-of-care setting, and pregnant at time of enrollment, will be prospectively enrolled prior to any pregnancy outcome. Women with insomnia disorder exposed to QUVIVIQ at any time during pregnancy or within 5 half-lives prior to conception will be assigned to Cohort A. Women with insomnia disorder who have been exposed to non-ORA medications for insomnia during pregnancy or within 5 half-lives of the respective insomnia medication prior to conception (Cohort B1) and women with insomnia who have not been exposed to any insomnia medication during pregnancy and within 5 half-lives of any insomnia medication taken prior to conception (Cohort B2) will comprise the comparator group (Cohort B).

Secondary data sources will be used to evaluate the rate of complications in parallel with external comparator cohort(s) representing the prevalence of birth defects in the general population [see Section 5.4.4]. To reduce bias that may occur if outcome information is known prior to enrollment, pregnant women should be enrolled in the study as soon as their pregnancy is known, prior to any informative prenatal testing (such as maternal serum screening or amniocentesis) where the knowledge of the primary study outcome of their pregnancy would be known – either normal or abnormal), and preferably in the first trimester before 20 weeks gestation.

Women who were exposed to QUVIVIQ during pregnancy or within 5 half-lives prior to conception, but for whom the outcome of pregnancy is known prior to enrollment (retrospective pregnancies), will be enrolled in this study and analyzed in a separate case series.

5.2.1 Patient eligibility

Women will be screened for eligibility criteria for each pregnancy, should they contribute more than one pregnancy in the registry. Any within-patient pregnancy correlations will be accommodated in the analysis as part of the SAP.

5.2.1.1 Eligibility criteria for prospective pregnancies

Inclusion criteria

- Diagnosis of insomnia disorder prior to pregnancy.
- Pregnancy is ongoing and outcome of pregnancy (i.e., pregnancy loss or live birth) is not known.
- One of the following:
 - Woman exposed to QUVIVIQ at any time during the current pregnancy or within 5 half-lives prior to conception.
 - Woman exposed to other, non-ORA medications for insomnia during pregnancy or within 5 half-lives of the respective insomnia medication prior to conception.

Confidential

- Woman unexposed to any insomnia medication during pregnancy and within
 5 half-lives of any insomnia medication taken prior to conception.
- Able and willing to consent to the conditions and requirements of the registry. If the patient is a minor, able and willing to consent/assent according to local regulations.
- Agrees to electronically sign the Release of Medical Information Form permitting the study staff to contact her HCPs (e.g., primary care provider, insomnia specialist, psychiatrist, obstetrician, nurse midwife) and the infant's HCP (e.g., pediatrician) for medical information.

Exclusion criteria

- Exposure to any ORA other than QUVIVIQ (including BELSOMRA® (suvorexant), DAYVIGO® (lemborexant), any ORA newly approved during the study period, or any ORA in pre-market clinical studies) during the current pregnancy or within 5 half-lives of the respective medication prior to conception.
- Woman is currently participating in an interventional study or has taken an investigational product within 3 months prior to conception or during the current pregnancy.

5.2.1.2 Eligibility criteria for retrospective pregnancies

Inclusion criteria

- Diagnosis of insomnia disorder prior to pregnancy.
- Pregnancy has ended.
- Woman exposed to QUVIVIQ during pregnancy or within 5 half-lives prior to conception.
- Able and willing to consent to the conditions and requirements of the registry. If the patient is a minor, able and willing to consent/assent according to local regulations.
- Agrees to electronically sign the Release of Medical Information Form permitting the study staff to contact her HCPs (e.g., primary care provider, insomnia specialist, psychiatrist, obstetrician, nurse midwife) and the infant's HCP (e.g., pediatrician) for medical information.

Exclusion criteria

- Exposure to any ORA other than QUVIVIQ (including suvorexant, lemborexant, any ORA newly approved during the study period, or any ORA in pre-marketing clinical studies) during pregnancy or within 5 half-lives of the respective medication prior to conception.
- Woman participated in an interventional study or took an investigational product within 3 months prior to conception or during the pregnancy.

5.3 Variables

5.3.1 Exposure definition and measures

Exposure information recorded will include start and stop dates, dose, dosing frequency, and reason for discontinuation (if applicable).

The following criteria will be used to assign women to one of the cohorts:

- Cohort A: Exposure to QUVIVIQ at any point during the patient's pregnancy or at any time within 5 half-lives prior to conception.
- Cohort B:
 - Cohort B1: No exposure to QUVIVIQ or any other ORA (including, suvorexant, lemborexant, any ORA newly approved during the study period, or any ORA in pre-marketing clinical studies) but exposure to another insomnia medication [Appendix 3] during pregnancy or within 5 half-lives of the respective medication prior to conception.
 - Cohort B2: No exposure to any insomnia medication during pregnancy and within
 5 half-lives of the insomnia medication taken prior to conception.

Women with retrospective pregnancies will be considered to have been exposed to QUVIVIQ if there is documentation of exposure to QUVIVIQ at any point during the patient's pregnancy or at any time within 5 half-lives prior to conception.

Exposure assessments will not be determined for the external comparator cohort(s), as patient-level data is not available; these cohorts represent the prevalence of birth defects in the general population.

5.3.2 Outcome definition and measures

All outcomes defined in this section will be assessed in Cohort A, Cohort B1, Cohort B2, and among women with retrospective pregnancies as patient-level data will be collected [see Table 2]. For the external comparator populations, the outcome of major congenital malformations will be analyzed as described in Section 5.7.4.3.

Table 2 Summary key outcome assessments across data sources

	Prospective pregnancies			Retrospective	MACDP and			
	Cohort A	Cohort B1	Cohort B2	pregnancies	EUROCAT ^a			
Primary Outcome								
Major congenital malformation	X	X	X	X	X			
Secondary Outcomes	Secondary Outcomes							
Pregnancy complications: preeclampsia, pregnancy-induced hypertension, preterm labor, gestational diabetes	Х	X	X	X				
Pregnancy outcomes: preterm birth elective or spontaneous termination, fetal death or stillbirth	Х	X	X	X	Xb			
Infant outcomes: minor congenital malformation, size for gestational age, low birth weight, death, hospitalization for serious illness, postnatal growth and development	X	X	X	X	X°			

^a Additional external comparator data sources may be used [see Section 5.4.4], but similar to MACDP, only aggregate data will be available for comparison to this registry.

5.3.2.1 Primary outcome

Major congenital malformations

Congenital malformations will be primarily classified according to the MACDP classification system [CDC 2021]. Adjudicated major congenital malformations will serve as the primary outcome in this study (minor malformations will be excluded from the primary analysis). The MACDP classification lists major and minor birth defects that are tracked by MACDP, as well as conditions that are never included and those that are only included under certain circumstances. The code is based on the International Classification of Diseases, 9th Revision, Clinical Modification and the British Paediatric Association

^b MACDP and EUROCAT contain information on gestational age and birth outcome, if a delivery record is available.

^c MACDP and EUROCAT contain information on birth weight, if a delivery record is available.

MACDP = Metropolitan Atlanta Congenital Defects Program; EUROCAT = European Surveillance of Congenital Anomalies.

Classification of Diseases. All major congenital malformations will also be classified according to the EUROCAT classification system, if different from MACDP classification.

The CC will obtain medical records from the hospital and/or clinic where the suspected anomaly was identified. The records will be de-identified by the CC and uploaded into the secure IQVIA Clinical Event Validation and Adjudication Endpoint Adjudication System. All documents will be compiled by Clinical Event Validation and Adjudication into a dossier for review by the independent teratologists. All potential major congenital malformations identified by the patient's HCPs or the infant's HCPs will be evaluated by a qualified, independent committee of at least 3 teratologists using all available medical records [see Section 10]. The classification of potential major congenital malformations will be based upon the teratologists' adjudication, who will be blinded to patient exposure status. The adjudication process will involve the classification of congenital anomalies by both MACDP and EUROCAT classification systems.

5.3.2.2 Secondary outcomes

5.3.2.2.1 Pregnancy complications

Preeclampsia

Primary preeclampsia will be based on HCP-reported diagnosis. It is defined as the presence of hypertension on 2 occasions at least 4 hours apart after 20 weeks gestation (in a woman with previously normal blood pressure) and proteinuria; or, in the absence of proteinuria, a new onset of hypertension accompanied by one of the following conditions: thrombocytopenia, renal insufficiency, impaired liver function, pulmonary edema, or cerebral or visual symptoms [ACOG 2019].

Pregnancy-induced hypertension

High blood pressure (elevated: systolic between 120–129 mmHg and diastolic less than 80 mmHg; Stage 1 hypertension: systolic between 130–139 mmHg or diastolic between 80–89 mmHg; Stage 2 hypertension: systolic at least 140 mmHg or diastolic at least 90 mmHg) associated with pregnancy, as diagnosed by the treating HCP [ACOG 2019].

Preterm labor

Preterm labor will be based on HCP-reported diagnosis. It is characterized as regular contractions of the uterus resulting in changes in the cervix that start before 37 weeks of pregnancy. Any interventions or treatments provided to the patient as a result of preterm labor will be collected.

Confidential

Gestational diabetes

Gestational diabetes will be based on HCP-reported diagnosis. It is characterized by the development of carbohydrate intolerance with first onset or first recognition during pregnancy. A record of an oral glucose tolerance test during pregnancy will also be accepted for data collection, where available [ACOG 2018].

5.3.2.2.2 Pregnancy outcomes

Elective or therapeutic pregnancy terminations

Elective or therapeutic pregnancy terminations are defined as any induced or voluntary fetal loss during pregnancy. If available, data from pathologic examination of the abortus or fetus will be evaluated by the Adjudication Committee [see Section 10] for structural or chromosomal defects. The reason for elective or therapeutic termination will be collected. Elective versus therapeutic terminations will be summarized separately.

Spontaneous abortions

A spontaneous abortion is defined as loss of a fetus due to natural causes at < 20 weeks of gestation. If available, information from gross or pathologic examination of the abortus or fetus will be evaluated by the Adjudication Committee [see Section 10] for structural and chromosomal defects.

Fetal death or stillbirth

Fetal death or stillbirth refers to the death of a fetus prior to birth at or after 20 weeks of gestation. In the event of a stillbirth or fetal death, full pathology details will be requested and examined for structural or chromosomal defects. The final classification between fetal death / stillbirth and spontaneous abortion will be based on gestational age.

Live birth

A live birth refers to a complete expulsion or extraction from its mother of a surviving neonate.

Preterm birth

A live birth will be classified as preterm prior to 37 weeks of gestation according to the CDC definition [cdc.gov_a]. Preterm birth will be categorized as early preterm (< 34 weeks), late preterm (34–36 weeks), and early term (37–38 weeks).

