5.3.2.2.3 Infant outcomes

Minor congenital malformations

Congenital malformations will be classified according to the MACDP classification system [see Section 5.4.4.1]. Minor congenital malformations are part of the secondary objectives for this study. All potential minor congenital malformations will be evaluated by at least 3 qualified, independent teratologists using all available medical records [see Section 10].

Confidential

The classification of potential minor congenital malformations will be based upon the teratologist's adjudication, who will be blinded to patient exposure status. Adjudicated minor congenital malformations will not be included in the analysis of the primary objective. All minor congenital malformations will also be classified according to the EUROCAT classification system, if different from MACDP classification.

Size for gestational age

All live births will be classified as small, appropriate, or large for gestational age using the World Health Organization definition [WHO 1995] of birth weight below the 10th percentile, between the 10th and 90th percentile, and above the 90th percentile for age, respectively.

Low birth weight

An infant with low birth weight will be classified as weighing under 2500 g [cdc.gov_b]. Low birth weight can be subclassified into very low birth weight (< 1500 g) and moderately low birth weight (1500 g to 2499 g).

Infant death

An infant death refers to the death of a live-born infant within the first year of life. Infant deaths will be subclassified as neonatal deaths (≤ 28 days of life) and infant deaths (29 to 365 days of life).

Hospitalization for serious illness

Hospitalizations for serious illness refer to in-patient admissions for treatment of potentially life threatening illnesses among live-born infants within the first year of life. Serious illnesses will be based on HCP-reported diagnosis.

Postnatal growth and development

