5.7.4.2 Analysis of primary and secondary endpoints

The prevalence of major and minor congenital malformations will be calculated using the MACDP convention. If needed for future analyses, minor and major congenital malformations will also be calculated using the EUROCAT convention using the same process. Major malformations will be analyzed separately from minor malformations, with the primary analysis including only adjudicated major congenital malformations. The total prevalence will be calculated by dividing the number of women with any adjudicated cases of each event (observed in live births, fetal deaths, elective or therapeutic terminations, and at any gestational age) by the total number of pregnancies (excluding spontaneous terminations and ectopic or molar pregnancies). The prevalence at birth will be calculated as number of cases observed in live births and stillbirths divided by the total number of births (stillbirths + live births). Data analysis for major congenital malformations will be based on exposure to QUVIVIQ from within 5 half-lives prior to conception through the end of the first trimester.

Confidential

The prevalence of pregnancy complications, including preeclampsia, pregnancy-induced hypertension, gestational diabetes, and preterm labor, will be summarized by dividing the number of pregnant women with that complication by the total number of pregnant women.

The prevalence of spontaneous abortions will be calculated by dividing the number of women with fetal loss occurring before 20 weeks gestation by the total number of pregnant women.

The prevalence of elective and therapeutic abortion will be estimated similarly as separate outcomes.

The prevalence of preterm birth will be calculated by dividing the number of cases by the total number of births (stillbirths + live births). The prevalence of small for gestational age will be calculated by dividing the number of cases by the total number of live births.

For other events of interest occurring in developing neonates and infants, including mortality, hospitalizations for serious illness, growth, and developmental delays, the prevalence will be calculated as the number of cases divided by the total number of live births.

The prevalence of primary and secondary outcome measures will be presented with 97.5% CIs for binomial proportion. The analyses summarized in this section will be performed on the Cohort A and Cohort B.

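### The definitions of live birth and preterm birth, and the preterm denominator, contradict other parts of the protocol, so early neonatal deaths can be lost and preterm births misclassified

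*Protocol*

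**What the plan says.** All three items concern secondary outcomes and stand in the current protocol text.

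- **Live birth** (5.3.2.2.2): "A live birth refers to a complete expulsion or extraction from its mother of a surviving neonate". The same section separates stillbirth by timing: "Fetal death or stillbirth refers to the death of a fetus prior to birth at or after 20 weeks of gestation". Section 5.3.2.2.3 then builds on live birth: "An infant death refers to the death of a live-born infant within the first year of life", and "Infant deaths will be subclassified as neonatal deaths (≤ 28 days of life) and infant deaths (29 to 365 days of life". For infant mortality and the other infant events, section 5.7.4.2 says "the prevalence will be calculated as the number of cases divided by the total number of live births".
- **Preterm categories** (5.3.2.2.2): "A live birth will be classified as preterm prior to 37 weeks of gestation according to the CDC definition". The next sentence reads "Preterm birth will be categorized as early preterm (< 34 weeks), late preterm (34–36 weeks), and early term (37–38 weeks". The synopsis puts births from 37 weeks onward under full-term live birth.
- **Preterm prevalence** (5.7.4.2): "The prevalence of preterm birth will be calculated by dividing the number of cases by the total number of births (stillbirths + live births". The sentence after it gives small for gestational age a denominator of live births only.

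**The concern.** These sentences fix how events are coded and counted, so a coordinating center that follows them literally gets a wrong or undefined answer.

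The live-birth wording is the most serious of the three. The pregnancy-outcome options at the delivery contact (5.6.1.2.2) are live birth, spontaneous abortion, stillbirth, and elective or therapeutic termination. The contact is scheduled about 4 weeks after the estimated delivery date (5.4.2), when staff will usually know whether the infant has died. For a death on day 2, no option clearly fits as written. If the infant is not coded as a live birth, the death leaves the infant-death numerator and the infant leaves the live-birth denominators. Infant follow-up contacts also fall away, because section 5.4.2 restricts them to live births. With several countries and about ten years of collection, inconsistent coding is a realistic risk.

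The two preterm defects are smaller. One makes the categories disagree with the outcome they subdivide. The other puts births that can never be cases into a denominator.

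**Working it through.** **Power check on the plan's own figure.** Table 4 (5.5.2), infant death at risk ratio 2.5: P_B = 2.9%, P_A = 1.05 × 2.9% = 3.045%, margin = 1.5 × 2.9% = 4.35%, and n = 102 (A), 204 (B1), 102 (B2), 306 (B). The one-sided level is 2.5%.

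- Power = Φ((margin − (P_A − P_B))/SE − 1.96), with the averaged variance of section 5.5.1.
- Averaged variance = (0.03045 × 0.96955 + 0.029 × 0.971)/2 = 0.02884.
- A vs B1: SE = √(0.02884 × (1/102 + 1/204)) = 0.02059; (0.0435 − 0.00145)/0.02059 − 1.96 = 0.08; power 53.3% (stated 53.5%).
- A vs B2: 42.4% (stated 42.3%). A vs B: 58.2% (stated 58.5%).

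The power figures reproduce closely. The defect is in the definitions, not in the power table.

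**1. Live birth.** Consider an infant born alive who dies on day 2.

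| Rule | Does the infant fit? |
|---|---|
| Live birth (5.3.2.2.2) | Only if *surviving* means alive at delivery |
| Stillbirth (5.3.2.2.2) | No, death was after birth |
| Neonatal death (5.3.2.2.3) | Yes, but only if live-born |
| Neonatal death at delivery contact (5.6.1.2.2) | Yes, collected |

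Expected infant deaths at 2.9%: Cohort A 102 × 0.029 = 2.96; Cohort B1 204 × 0.029 = 5.92. One death is therefore about a third of Cohort A's expected events (1/2.96 = 0.34). As an illustration, take 3/102 against 6/204, a risk ratio of 1.00. Losing one Cohort A infant from numerator and denominator gives 2/101 = 1.98% against 2.94%, a risk ratio of 0.67.

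**2. Preterm categories.** The classes below 34 weeks and 34–36 weeks already cover everything under 37 weeks. Adding 37–38 weeks makes the three classes sum to births before 39 weeks, while the defined outcome is births before 37 weeks. A birth at 37 weeks is then full term in the synopsis and sits in a preterm category in 5.3.2.2.2.

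**3. Preterm denominator.** Inputs: live birth 62% (5.5.1), stillbirth 1.4% and premature birth 11.0% (Table 4). Taking 62% and 1.4% as shares of all pregnancies, and 11.0% as a share of live births:

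- Dilution factor = 0.62/(0.62 + 0.014) = 0.978.
- 11.0% × 0.978 = 10.76%, that is 0.24 points or 2.2% relative.
- If 1.4% is instead a share of all births, 11.0% × 0.986 = 10.85%.

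The risk ratio is multiplied by the ratio of the two cohorts' dilution factors.

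- Equal live-birth and stillbirth rates in both cohorts: ratio 1, no effect.
- Table 4's planning values for Cohort A (live birth 60.1%, stillbirth 1.47%): 0.601/0.6157 = 0.976; 0.976/0.978 = 0.998, a shift of about 0.2%.
- Stillbirth three times as frequent in Cohort A (4.2%), live birth held at 62%: 0.62/0.662 = 0.937; 0.937/0.978 = 0.958, so the preterm risk ratio would read about 4% too low.

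**The case against.** The best defence of the live-birth sentence is that it describes the moment of delivery and sets no survival period, so alive at delivery is a natural reading. It matches the stillbirth definition in the same section, and the rest of the protocol supports it: the synopsis lists death under initial neonatal information, section 5.3.2.2.3 classifies deaths up to 28 days, and section 5.6.1.2.2 collects them. This largely stands as evidence of intent. It does not repair the sentence, which a coder can follow literally and which cites no standard definition.

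On the preterm categories, the cut-off below 37 weeks appears in both the synopsis and section 5.3.2.2.2, and the extra class is itself named as a term class. That also stands: the total should not include it. The contradiction inside the definition remains.

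On the denominator, the synopsis does not restrict preterm birth to live births, so perhaps preterm stillbirths were meant to count. Section 5.3.2.2.2 says otherwise, and the two sections must agree. The numerical effect is small.

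Four stronger inferences are tempting but unsupported.

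- That early neonatal deaths are definitely excluded: only one of two readings does that.
- That the early and late neonatal mortality figures in section 5.4.4.2 show how many deaths would be lost: by its title in the reference list, that study concerns pregnancies complicated by major congenital anomalies. The protocol gives no neonatal share for its own 2.9%.
- That reported preterm prevalence will be greatly inflated: this requires ignoring the stated cut-off and assuming a rate of 37–38-week births that the protocol does not give.
- That the primary comparison loses malformed infants who die early: section 5.7.1.3 includes adjudicated malformations reported up to 1 year by the mother or a healthcare provider, and the total-prevalence denominator in 5.7.4.2 is pregnancies, not live births. On the strict reading, the denominator affected is that of the separate prevalence at birth; the total-prevalence numerator list would merely fail to name such an infant.

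**Conclusion.** The point holds as an internal inconsistency in three secondary-outcome rules.

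- **Live birth:** early neonatal deaths can be lost, depending on how *surviving* is read. The number at risk cannot be derived from the protocol, but with about 3 expected infant deaths in Cohort A and 6 in B1, a single miscoded case is visible in the result.
- **Preterm categories:** the listed classes do not add up to the defined outcome. The total is wrong only if someone sums them.
- **Preterm denominator:** prevalence is understated by about 2% relative on the protocol's planning rates (11.0% to about 10.76%). The risk ratio moves only if the share of stillbirths among births differs between cohorts.

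The sample size and the Table 4 power figures do not change. The case for correcting the text is that the definitions conflict as written and govern a long, multi-country data collection; it does not rest on a demonstrated large bias.

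**What to change.** Amend the wording in three places:

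1. In 5.3.2.2.2, define live birth as delivery of an infant born alive, whatever the later survival. State in 5.3.2.2.3 that any later death up to 365 days counts as infant death, and add one matching eCRF completion instruction for the pregnancy-outcome field.
2. In 5.3.2.2.2, take 37–38 weeks out of the preterm categories and, if it is wanted, report it as a subclass of term birth.
3. In 5.7.4.2, use live births as the denominator for preterm birth, as is already done for small for gestational age.

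The cost is a text amendment and the eCRF instruction. No new data, sample-size change or power recalculation is needed. Any delivery followed by an early death that has already been recorded should be checked once for consistent coding.
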